3.0 Study Design

This study will contain 2 cohorts, those with normal serum 25(OH)D and those with low serum 25(OH)D at enrollment. The study will take place in women with ovarian, primary peritoneal, and fallopian tube cancer, subsequently referred to as ovarian cancer in this document due to the overlap in disease and treatment.

Patients who have given written consent to enroll in the study will have a serum 25(OH)D drawn in a gold-topped tube (1 to 5mL volume) at time of enrollment and prior to initiation of treatment for their cancer. Serum 25(OH)D levels will be analyzed per laboratory protocol in our University CLIA certified lab. Blood will also be drawn for analysis of serum leptin levels and VDR *FokI* SNP genotype. A purple-topped tube (7 to 10mL volume) and red-topped tube will be collected from prospective patients. The Stephenson Cancer Center Biospecimen Bank will process the red and purple-topped tube into plasma and Buffycoats, label them with a de-identified code and transfer them to [name] lab. The plasma

will be used to evaluate leptin by ELISA and the Buffycoats used to evaluate the *FokI* SNP using PCR. Retrospective serum specimens will be used to measure leptin.

Patients with low serum vitamin D levels, defined as <20 ng/mL, will be provided a supply of cholecalciferol (vitamin D3), 50,000 IU weekly for 8 weeks that will be dispensed in the Stephenson Cancer Center outpatient pharmacy in order to standardize therapy. They will then be provided with a prescription for 2,000 IU of cholecalciferol (vitamin D3) daily following completion of 8 weeks of therapy based on current Endocrine Society guidelines in agreement with U.S. Preventive Services Task Force recommendations [14]. Treatment with cholecalciferol will not impact initiation of treatment for ovarian cancer. Compliance with cholecalciferol repletion will be assessed with medication reconciliation at every gynecologic oncology visit.

Vitamin D therapy will be stopped in any patient developing the above exclusion criteria of GFR <30, inability to tolerate oral medications, malabsorption syndrome, or primary hyperparathyroidism. In the unlikely event of evidence of vitamin D toxicity, treatment with vitamin D will be stopped. The Stephenson Cancer Center laboratory defines vitamin D toxicity as levels >100 ng/mL. Based on IOM literature, it would highly unlikely for individuals to experience vitamin D toxicity at the prescribed doses. Symptoms of vitamin D intoxication are caused by the resultant hypercalcemia and include anorexia, weight loss, polyuria, arrhythmias, fatigue, and soft tissue calcifications [20]. Patients experiencing these symptoms would receive testing for serum calcium and vitamin D. Vitamin D treatment would be stopped for any value indicative of toxicity.

Demographic, clinical, and disease characteristics and outcomes will be collected from all patients prospectively. The patient's treatment course information will also be collected prospectively, but will not be dictated by this study. Serum 25(OH)D and leptin levels will be collected again at the completion of primary therapy, 6 months after the completion of primary therapy, and at the time of disease recurrence. If disease recurrence occurs prior to 6 months after completion of primary therapy, this time point will be omitted. If disease recurrence does not occur prior to 1 year, serum 25(OH)D and leptin levels will be drawn at the time of the 1-year surveillance visit. If patients remain vitamin D deficient at any of these follow-up time points, they will be referred to an endocrinologist or primary care physician for further work-up and treatment of their vitamin D deficiency. Patients who are vitamin D deficient at completion of therapy but were not previously on supplement will be

IRB NUMBER: 7488
IRB APPROVAL DATE: 11/23/2021

referred to a primary care physician for further management. Data collection will continue for 1 year or until the time of disease recurrence. Patient's will no longer have data collected after obtaining serum 25(OH)D and leptin levels at the time of recurrence. A retrospective cohort of women with low serum 25(OH)D that did not receive repletion of vitamin D will be used as a control group for comparison. This control group will be identified from available tumor bank serum samples including those previously identified in the above-mentioned unpublished study at the University of Oklahoma. These samples will be used to evaluate serum levels of 25(OH)D, leptin, and evaluate Buffycots VDR SNP polymorphism for *FokI*.

Cohort	Therapy
1 (Normal 25(OH)D)	None
2 (Low 25(OH)D (<20ng/mL)	50,000 IU cholecalciferol weekly for 8 weeks followed by 2,000 IU daily thereafter

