1.2 Objective(s)

1.2.1 Primary objective:

1.2.1.1 To assess treatment-related morbidity (including 30-day postoperative surgical morbidity and chemotherapy-related morbidity) and 1-year disease-free survival in patients with deficient serum 25(OH)D levels at the time of ovarian, primary peritoneal, or fallopian tube cancer diagnosis who did and did not receive vitamin D repletion.

1.2.2 Secondary objectives:

1.2.2.1 To describe serum 25(OH)D levels, serum leptin levels, and VDR *FokI* SNP status among newly diagnosed ovarian, primary peritoneal, or fallopian tube cancer patients.

1.2.2.2 To determine the proportion of patients with ovarian, primary peritoneal, or fallopian tube cancer that have deficient vitamin D at diagnosis and have normal serum 25(OH)D after oral vitamin D supplementation during primary therapy.

1.2.2.3 To identify potential relationships between serum 25(OH)D and serum leptin levels when controlling for BMI.

1.2.2.4 To evaluate change of serum leptin levels with repletion of 25(OH)D in patients with low levels at the time of ovarian primary peritoneal, or fallopian tube cancer diagnosis.

1.3 Translational Research Objectives:

1.3.1 To evaluate VDR *FokI* SNP status relationship with serum 25(OH)D levels and treatment-related morbidity and cancer outcomes.

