8.0 Study Parameters

8.1 Observations and Tests

The following observations and tests are to be performed and recorded on the appropriate form(s).

Observation and Tests	Screening	At each treatment visit	Completion of primary therapy	6 months after therapy completion	Time of recurrence or 1 year surveillance (if no recurrence)
History & Physical	1	X	X	X	X
Vital Signs and Weight	1				
Toxicity assessment	1	X	X	X	
Serum 25(OH)D	1		X	X	X
Serum Leptin	1		X	X	X

Serum Cr (and GFR)	1				
Red top and Purple topped blood tubes (for VDR SNP analysis)	1				
Serum pregnancy test (if potential exists)	1				

1. Must be obtained within 21 days prior to initiating protocol therapy.

All other blood draws (end of treatment, 6 months after therapy completion, Time of recurrence or 1 year surveillance) must occur within 8 weeks of expected date.

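### The protocol contradicts itself on the leptin specimen; if section 3.0 is followed, prospective women are assayed in plasma and historical controls in serum, and a leptin difference between the two sources cannot be interpreted

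*Protocol*

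**What the plan says.** The only laboratory instructions for leptin are in Protocol 3.0 (Study Design). For prospective patients, the biospecimen bank "will process the red and purple-topped tube into plasma and Buffycoats". The plasma "will be used to evaluate leptin by ELISA and the Buffycoats used to evaluate the *FokI* SNP using PCR". The next sentence turns to the controls: "Retrospective serum specimens will be used to measure leptin". Further on in 3.0, the source of the controls is given: "This control group will be identified from available tumor bank serum samples". Their use is then stated: "These samples will be used to evaluate serum levels of 25(OH)D, leptin", with FokI typed from buffy coat.

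Elsewhere the measure is called serum leptin:

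- Objective 1.2.2.1 reads "To describe serum 25(OH)D levels, serum leptin levels", and objectives 1.2.2.3 and 1.2.2.4 use the same term. The SAP objectives repeat it.
- Section 3.0 itself introduces the prospective draw as one for serum leptin.
- The schedule in 8.1 has one serum leptin row covering screening and all follow-up points. A separate row, marked at screening only, is labelled "Red top and Purple topped blood tubes (for VDR SNP analysis".
- Protocol 12.0 and SAP section 5a compare the leptin-25(OH)D association among groups. BMI is the only stated adjustment.

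Neither document mentions paired plasma and serum samples, calibration between them, or a term for specimen type.

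**The concern.** A laboratory that follows 3.0 will run plasma for every prospective woman and serum for every historical control. Protocol 3.0 makes those historical women the comparison group and has leptin measured in them, and 12.0 compares leptin among groups. A repleted versus non-repleted leptin contrast is therefore a natural secondary result, although it is not written as a separate hypothesis. Any systematic difference between plasma and serum readings would appear in full as a difference between the two sources, and enrolling more patients would not reduce it.

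The pooled leptin-25(OH)D analysis has a related problem. All historical controls are vitamin D deficient by selection, while prospective women span normal and low values. Specimen type is therefore correlated with 25(OH)D once the sources are combined, and an offset can enter the slope.

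The choice of specimen is hard to reverse, because blood already processed to plasma cannot be turned back into serum.

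**Working it through.** **The plan's own figure.** The documents give no design figure for leptin. The one they give is 80% power for chemotherapy delay, 33% versus 65%, with 25 and 75 patients. Two-sided alpha of 0.05 is assumed, since none is stated. With 33% in the group of 25:

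- Pooled proportion = (25×0.33 + 75×0.65)/100 = 0.57.
- Null SE = √(0.57×0.43×(1/25 + 1/75)) = 0.1143.
- Alternative SE = √(0.33×0.67/25 + 0.65×0.35/75) = 0.1090.
- Power = Φ((0.32 − 1.96×0.1143)/0.1090) = 81.1%. With the rates exchanged it is 81.3%.

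The stated 80% is reproduced. It does not bear on leptin; only the group sizes carry over.

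**Specimen by source, if 3.0 is followed.**

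- Prospective, normal 25(OH)D: plasma at baseline.
- Prospective, low 25(OH)D, repleted: plasma at baseline.
- Historical, low 25(OH)D, not repleted: serum.
- Prospective follow-up samples: specimen not settled. The processing text in 3.0 concerns the red and purple tubes, which 8.1 lists at screening only. The leptin row in 8.1 says serum throughout.

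**Mean difference between sources.** Write leptin = a + δ·source + τ·specimen + β·BMI. With source and specimen identical for all 25 + 75 women, the design matrix has 4 columns and rank 3. Only δ + τ can be estimated, and BMI adjustment does not help.

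**Normal versus low 25(OH)D.** Take 75 normal prospective, 25 low prospective and 75 historical women. The model with intercept, low status and source has 3 columns and rank 3, so the low-versus-normal effect is estimable once a source term is present. Adding specimen type gives 4 columns and still rank 3.

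**Leptin-25(OH)D slope.** With a separate intercept for each source, a constant offset is absorbed and the slope is estimated within source. If the offset is proportional, the same holds on the log scale. Without a source term it is not absorbed.

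**Illustration of size (offsets assumed).** With no true leptin difference and an offset of b standard deviations, SE = √(1/25 + 1/75) = 0.231 SD. The rejection rate is 1 − Φ(1.96 − b/0.231) + Φ(−1.96 − b/0.231).

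- b = 0: 5%
- b = 0.1: 7%
- b = 0.2: b/0.231 = 0.866, giving 0.137 + 0.002 = 14%
- b = 0.3: 26%
- b = 0.5: 58%

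**The case against.** The strongest reply is that serum was intended throughout and the plasma wording in 3.0 is a slip. The objectives, the schedule, the analysis text and the opening of the prospective blood-draw description all say serum leptin, and 8.1 assigns the red and purple tubes to SNP typing. If prospective leptin is in fact run on serum, the specimen problem disappears. That is fair, and it means the documents establish a contradiction, with aliasing as the consequence of following one side of it. It does not remove the need to act: 3.0 is the only text that tells the laboratory what to do, and it names no serum fraction from those tubes.

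Two stronger readings are tempting and are not supported.

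- A reader might infer that specimen type is aliased with the study's Cohorts 1 and 2. Both are prospective and share a specimen type, so the aliasing is with prospective versus historical source only.
- A reader might infer that the change in leptin with repletion (objective 1.2.2.4) is measured in plasma at baseline and serum afterwards. The schedule has one leptin row for all time points, and nothing announces a change of specimen. The risk is real only if follow-up samples are handled differently, which the documents do not say.

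It is also true that leptin is secondary, that the prospective-versus-historical leptin contrast is implied rather than specified, and that a source term protects the slope in objective 1.2.2.3 against a constant offset. These points limit the importance of the problem; they do not rescue the mean comparison.

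**Conclusion.** The protocol's statements on the leptin specimen conflict and must be reconciled. Under the operative text of 3.0, the mean leptin difference between repleted women and historical controls is completely confounded with specimen type, and no covariate can separate them. A pooled leptin-25(OH)D analysis is exposed as well unless it carries a source term. Normal versus low 25(OH)D among prospective women is sound on this point. Within-patient change is sound if one specimen type is used throughout.

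The confounding is certain if 3.0 is followed; bias is possible but not shown. The size and direction of any plasma-serum offset are not in the documents, so the rejection rates of 7% to 58% for 0.1 to 0.5 SD illustrate sensitivity and are not estimates. The change should be made, but the primary objective does not depend on it.

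**What to change.** Amend Protocol 3.0, and align 8.1 with it, as follows.

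- Process the red-topped tube, already drawn at screening, to serum, and keep the purple-topped tube for buffy coat and FokI typing. The laboratory should confirm that the red-topped tube contains no anticoagulant, because the protocol does not say.
- Run leptin in serum for prospective and historical women and at every time point, with the same kit and with both sources mixed within assay batches. Name the tube for the follow-up leptin draws.
- In Protocol 12.0 and SAP section 5a, include a source indicator in any model that pools prospective and historical women for leptin and 25(OH)D.
- If only plasma was kept for women already enrolled, limit leptin inference to same-specimen comparisons. A subset with paired plasma and serum, to estimate the offset, is an alternative.

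The cost is a protocol amendment with IRB review, revised laboratory instructions, and holding prospective serum until it can be batched with control samples. No extra patients, no extra screening tube and no additional leptin time points are needed. Using one specimen type does not make the sources fully comparable: the controls come from earlier years, so storage time and calendar period stay confounded with source and should be stated as a limitation.

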10.0 Duration of Study

10.1 Patients with serum 25(OH)D $<20\text{ng/mL}$ will receive cholecalciferol 50,000 IU weekly for 8 weeks.

10.2 Following repletion, patients will receive a prescription for 2,000 IU cholecalciferol as maintenance. Per Endocrine Society guidelines, patients should continue maintenance cholecalciferol indefinitely.

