## 2. Design information

### a. General statistical considerations

This study will contain 2 cohorts, those with normal serum 25(OH)D and those with low serum 25(OH)D at enrollment. The study will take place in women with ovarian, primary peritoneal, and fallopian tube cancer, subsequently referred to as ovarian cancer in this document due to the overlap in disease and treatment.

Patients with low serum vitamin D levels, defined as <20 ng/mL, will be provided a supply of cholecalciferol (vitamin D3), 50,000 IU weekly for 8 weeks that will be dispensed in the Stephenson Cancer Center outpatient pharmacy to standardize therapy. They will then be provided with a prescription for 2,000 IU of cholecalciferol (vitamin D3) daily following completion of 8 weeks of therapy. Treatment with cholecalciferol will not impact initiation of treatment for ovarian cancer. Compliance with cholecalciferol repletion will be assessed with medication reconciliation at every gynecologic oncology visit.

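### Vitamin D must be stopped if GFR falls below 30, but creatinine/GFR is scheduled only at screening and no later value is required

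*Protocol*

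**What the plan says.** Protocol 3.0 sets the rule: "Vitamin D therapy will be stopped in any patient developing the above exclusion criteria of GFR <30". The same sentence adds oral intolerance, malabsorption and primary hyperparathyroidism. Entry requires a GFR of at least 30 (Protocol 4.2.2.1), so a patient may start at the stopping threshold.

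The table in Protocol 8.1 has a row beginning "Serum Cr (and GFR" whose only mark is in the screening column. The footnote to that mark reads "Must be obtained within 21 days prior to initiating protocol therapy".

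Other blood tests are repeated. Protocol 3.0 states "Serum 25(OH)D and leptin levels will be collected again at the completion of primary therapy, 6 months after the completion of primary therapy", and again at recurrence, or at 1 year if there is none.

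Dosing does not end with the loading course. Patients move to 2,000 IU daily, and Protocol 10.2 says "Per Endocrine Society guidelines, patients should continue maintenance cholecalciferol indefinitely".

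Protocol 3.0 also says that the cancer treatment course is collected but not determined by the study.

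**The concern.** A stopping rule defined by a laboratory threshold works only if someone has the laboratory value. Of the four conditions in the sentence, GFR below 30 is the only one set by a number, and a history, physical examination or pill count cannot establish it. At entry the protocol did not leave the same threshold to routine care; it scheduled the test. After entry it keeps the threshold but schedules nothing to check it against.

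What is at stake is participant safety: a repleted patient whose renal function falls could continue cholecalciferol when the protocol says she must stop, without any departure from the schedule. Protocol 5.1.1 says that the drug is converted to its active metabolite by the kidney, so renal function is relevant on the protocol's own account.

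**Working it through.** The plan gives no figure on this point to reproduce. The check sets the rule against every place that could supply its input.

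**1. The schedule (Protocol 8.1)**

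| Item | Screening | Each treatment visit | Completion | 6 months | Recurrence / 1 year |
|---|---|---|---|---|---|
| Creatinine/GFR | yes | – | – | – | – |
| Serum 25(OH)D | yes | – | yes | yes | yes |
| Serum leptin | yes | – | yes | yes | yes |
| Toxicity assessment | yes | yes | yes | yes | – |
| History and physical | yes | yes | yes | yes | yes |

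Creatinine/GFR is marked in 0 of the 4 post-screening columns; 25(OH)D and leptin are marked in 3 of the 4. The blank cells are unlikely to be a fault in reading the table, because they agree with the footnote and with the neighbouring screening-only rows.

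**2. Other places that might require a value**

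- Toxicity assessment: no laboratory test is named, and the row is unmarked at recurrence/1 year.
- Protocol 7.0: only the 25(OH)D limit of 100 ng/mL appears.
- Protocol 11.1 and 11.2: adverse events are graded and reported, and the monitoring committee reviews accumulated safety data twice a year. Test results may be obtained to supplement an adverse event report, but none is required.
- SAP 5b, 8a and 9: pill counts, adverse event tables and reasons for missing data. No renal value is called for.

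None of these requires a creatinine to be obtained, recorded or compared with 30.

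**3. Age of the only required value**

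Inputs: screening 0 to 21 days before the first dose (Protocol 6.2.1 and 8.1); eight weekly doses (Protocol 6.3).

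- Dose 8 falls 7 × 7 = 49 days after dose 1. Age of the screening GFR: 49 + 0 = 49 to 49 + 21 = 70 days.
- At day 365 from dose 1, for a patient still on maintenance: 365 + 0 = 365 to 365 + 21 = 386 days. Taking dose 1 as the origin is an assumption; the protocol does not say from when the 1-year visit is counted. If it is counted from the end of primary therapy, the value is older.

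**4. Cost of closing the gap at follow-up**

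Inputs: 3 existing follow-up draws; at least 25 repleted patients (Protocol 12.0).

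- 3 × 25 = 75 assays. As 25 is a floor, the general figure is 3 × (number repleted).
- A patient who recurs before the 6-month visit skips that visit and has fewer than three.

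**The case against.** The strongest reply is that the sentence works on clinical discovery. No specific test is scheduled for the other three conditions either; the study does not dictate cancer care; it describes repletion as standard of care; and patients on chemotherapy may well have creatinine measured anyway. Adverse event reporting and committee review add further routes by which a low GFR could surface. This is a fair reading, and it limits the size of the point. It does not remove it: these routes may reveal a fall, but nothing obliges anyone to look or to apply the rule. They are also least assured after primary therapy, when daily dosing continues.

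Stronger readings that a reader might infer are not supported:

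- *The vitamin D safety plan has no trigger.* It has others. 25(OH)D is measured at three later points, treatment stops above 100 ng/mL, and the protocol calls toxicity highly unlikely at these doses.
- *The symptom pathway is defective because it omits creatinine.* "Patients experiencing these symptoms would receive testing for serum calcium and vitamin D" serves a separate rule about hypercalcemia and toxicity, for which those are the relevant tests.
- *Most of the dose, and so most of the risk, falls after loading.* Cumulative dose is not risk. Maintenance is 7 × 2,000 = 14,000 IU per week against 50,000 IU in loading, or 28%.
- *The SAP is at fault for not tabulating stops by reason.* That is a reporting preference in a group planned at about 25. The SAP provides that "Compliance with cholecalciferol repletion will be assessed with medication reconciliation at every gynecologic oncology visit", and adds pill counts, so a stop may be visible in the patient's record.

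**Conclusion.** The point holds for the GFR rule alone. As written, the rule has no required input after screening, and dosing under it continues beyond primary therapy. The change is worth making because it is specific and cheap, but it is a modest safety improvement.

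Its size is the count of scheduled values: one at screening and none afterwards. The documents give no incidence of GFR below 30 and do not say how often routine care measures creatinine, so neither a number of missed stops nor a harm rate can be derived, and none is claimed.

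There is no effect on the primary comparison or on the stated 80% power, whose inputs (25 and 75 patients, 33% and 65% chemotherapy delay) contain no renal quantity.

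**What to change.** **Protocol 8.1, creatinine/GFR row.** Mark completion of primary therapy, 6 months after completion, and recurrence/1 year, with a footnote to this effect: *Cohort 2 patients still taking cholecalciferol. Run at the existing 25(OH)D/leptin draw unless a routine-care result from within the visit window is available. At treatment visits, record and review the routine-care creatinine when one exists; no extra draw is required.* The existing window of 8 weeks around the expected date can serve.

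**Protocol 3.0, after the stopping sentence.** Add: *Creatinine/GFR values from these visits are reviewed to apply the GFR <30 rule; if vitamin D is stopped, the date and reason are recorded.*

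**Cost.** About 3 assays per repleted patient: about 75 for 25 patients, more if more than 25 are deficient, and fewer where routine care already supplies a result. A slightly larger tube may be needed, since the protocol gives tube volumes only for enrollment. A few eCRF fields are added for the value, its date, and the stop date and reason.

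**What remains open.** A patient with no routine bloods during chemotherapy would still have no value until completion of primary therapy. Closing that as well would mean extra draws at treatment visits, which this proposal does not ask for.

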2.3 Leptin and Ovarian Cancer

Leptin is an adipokine that appears to stimulate growth of cancer cells while decreasing apoptosis [10]. Serum leptin levels have also been linked to elevated levels of pro-inflammatory cytokines in malignancy [11]. Retrospective analysis of data from NHANES III revealed an inverse relationship between serum leptin levels and cancer death in women [12]. In ovarian cancer, there is some data to show that lower leptin levels may be associated with increased initial tumor burden and subsequent increases in leptin may correlate with complete cytoreduction [13]. Further study is needed to better understand the role of leptin in ovarian cancer. Vitamin D receptors are involved in production of adipokines such as leptin; however, the response of serum leptin levels to repletion of vitamin D remains unclear [1]. Conflicting data exists between meta-analyses investigating changes in leptin following correction of vitamin D levels in humans [1]. This study aims to assess for potential relationships between serum 25(OH)D levels and leptin levels, including any changes that may occur during repletion of 25(OH)D.

Women with treatment-related morbidity often experience delays in treatment, changes in chemotherapeutic regimens and surgical or chemotherapy-related complications requiring hospitalization. Identifying modifiable risk factors among patients with ovarian cancer (including fallopian tube and primary peritoneal cancer) that can prevent treatment-related morbidity represents an important goal in the care of these women.

Safety:

Cholecalciferol is a generally safe and well-tolerated medication. Repletion of vitamin D is considered standard of care and will be undertaken utilizing current available guidelines [14].

Translational Research Background:

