4.2 Inclusion Criteria (Prospective patients)

4.2.1 Patients must have a histologic diagnosis of ovarian, fallopian tube, or primary peritoneal carcinoma per pre-treatment biopsies by laparoscopy, or interventional radiology, paracentesis, or CT guided core biopsy. Histologic documentation of the original primary tumor is required via the pathology report.

4.2.2 Patients must have adequate:

4.2.2.1 Renal function: Glomerular Filtration Rate (GFR) ≥ 30 .

4.2.2.2 Gastrointestinal absorption: No underlying malabsorption syndrome (i.e. inflammatory bowel disease, celiac disease).

4.2.2.3 Ability to tolerate oral medication.

4.2.3 Patients taking vitamin D at the time of enrollment without a diagnosis of vitamin D deficiency.

4.2.4 Patients of childbearing potential must have a negative pregnancy test prior to the study entry and be practicing an effective form of contraception. If applicable, patients must discontinue breastfeeding prior to study entry.

4.2.5 Patients must have signed an IRB-approved informed consent and authorization permitting release of personal health information.

4.2.6 Patients must be at least 18 years old.

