4.3 Ineligible Patients

4.3.1 Patients with a known pre-existing diagnosis of vitamin D deficiency.

4.3.2 Patients with renal disease and a GFR < 30 .

4.3.3 Patients with primary hyperparathyroidism.

IRB NUMBER: 7488
IRB APPROVAL DATE: 11/23/2021

4.3.4 Patients with other invasive malignancies, with the exception of nonmelanoma skin cancer. Patients with concomitant endometrial cancer diagnosed at the time of their ovarian cancer are allowed to participate if the endometrial cancer is FIGO stage IB or less.

4.3.10 Patients of childbearing potential, not practicing adequate contraception, patients who are pregnant, or patients who are breastfeeding are not eligible for this trial.

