5.1.2 Storage

Unopened vials of cholecalciferol are stable for the life indicated on the package stored at 15°C to 30°C (59°F to 86°F).

Adverse Effects: Consult the package inserts for the most current and complete information. No adverse reactions currently listed in manufacturer's labeling. According to the IOM, vitamin D toxicosis is highly unlikely at the prescribed doses. Symptoms of vitamin D toxicosis are caused by the resultant hypercalcemia and include: anorexia, weight loss, polyuria, arrhythmias, fatigue, and soft tissue calcifications [15].

Consult the American Hospital Formulary Service Drug Information guide, Facts and Comparisons, or the package insert for additional information.

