6.3 Sequence and timing of drug administration

Vitamin D deficient patients will receive oral cholecalciferol 50,000 IU weekly starting at the time of diagnosis of vitamin D deficiency. Initiation of cholecalciferol therapy will not delay initiation of standard treatment for ovarian cancer, nor will it preclude enrollment in other clinical trials. Therapeutic dosing at 50,000 IU will continue weekly for a total of 8 weeks. Patients will then be given a prescription for maintenance dosing 2,000 IU cholecalciferol thereafter.

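### No serum calcium is scheduled before vitamin D loading and the stop rule has no numeric calcium limit, so silent hypercalcemia has no study-required check before the first dose

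*Protocol*

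**What the plan says.** **Route of harm.** Protocol section 5.1.2 states: "Symptoms of vitamin D toxicosis are caused by the resultant hypercalcemia". Section 3.0 says the same and lists the symptoms: anorexia, weight loss, polyuria, arrhythmias, fatigue and soft tissue calcification.

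**Calcium testing.** Section 3.0 provides for it after symptoms: "Patients experiencing these symptoms would receive testing for serum calcium and vitamin D". It then says: "Vitamin D treatment would be stopped for any value indicative of toxicity". No calcium figure follows. Sections 3.0 and 7.0 give one numeric definition of toxicity, a vitamin D level above 100 ng/mL.

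**Eligibility and stopping.** Section 4.3.3 excludes "Patients with primary hyperparathyroidism", and SAP section 3c repeats this. Section 3.0 stops vitamin D if GFR falls below 30, or for "inability to tolerate oral medications, malabsorption syndrome, or primary hyperparathyroidism".

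**Start of dosing.** Section 6.3: "Vitamin D deficient patients will receive oral cholecalciferol 50,000 IU weekly starting at the time of diagnosis of vitamin D deficiency". Section 6.2.1 requires baseline evaluations before dosing. Section 8.1 lists them, and calcium is not among them.

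**Reasons for light monitoring.** The safety paragraph in section 2.3 says: "Repletion of vitamin D is considered standard of care". Section 7.0 describes toxicity at these doses as very rare.

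**The concern.** The plan identifies calcium as the harmful intermediate but does not look at it before giving the drug. The protocol's reassurance concerns toxicity caused by the dose. It does not address calcium that is already high for another reason when loading begins.

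Undiagnosed primary hyperparathyroidism is the clearest case, because the protocol itself regards the condition as a reason not to give vitamin D. An exclusion with no test behind it works only for women whose diagnosis is already known.

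What is at stake is the safety of an individual participant, together with consistent use of the stop rule. Without a stated calcium value, two investigators could act differently on the same result.

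**Working it through.** There is no figure in the plan to reproduce. The check sets the relevant provisions side by side and then sizes the remedy.

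**1. Laboratory tests required before the first dose (8.1, screening column).** 25(OH)D, leptin, creatinine with GFR, tubes for VDR genotyping, and a pregnancy test where relevant. Scheduled calcium measurements: 0.

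**2. Two exclusions compared.**

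| Exclusion | Test in 8.1 that applies it |
|---|---|
| GFR below 30 (4.3.2) | Screening creatinine and GFR |
| Primary hyperparathyroidism (4.3.3) | None |

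Hypercalcemia from other causes is not an exclusion.

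**3. Can the numeric limit catch the case at baseline?** Loading is given only when 25(OH)D is below 20 ng/mL (3.0). The toxicity limit is above 100 ng/mL (3.0, 7.0). No woman can satisfy both on her screening sample, so the limit cannot detect high calcium of another origin before the first dose.

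**4. Path through the plan.** Take a woman with 25(OH)D below 20 ng/mL, no symptoms and unrecognised high calcium. She passes section 4.3, completes the 8.1 screening tests without a calcium, and starts 50,000 IU weekly under 6.3. A calcium test becomes a study requirement only if she develops listed symptoms.

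**5. Exposure.** 8 × 50,000 = 400,000 IU over 56 days. 400,000 / 56 = 7,143 IU per day on average, and 7,143 / 2,000 = 3.6 times the maintenance dose. This describes what would be given. It is not evidence of hazard, since the regimen is the one the protocol ties to its cited guideline.

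**6. Size of the remedy.** Section 12.0 anticipates 100 enrolled and presumes at least 25 deficient.
- Calcium at screening in deficient women only: about 25 assays, and more if more women prove deficient.
- Calcium at screening in all women: 100 assays.
- Each repleted woman whose vitamin D is stopped: 1 / 25 = 4% of the planned repleted group.

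**7. Illustration only.** The documents give no hypercalcemia rate. If a proportion p of deficient women had unrecognised high calcium, the chance of at least one among 25 is 1 − (1 − p)^25. This gives 22% for p = 1%, 40% for p = 2% and 72% for p = 5%. These values of p are assumptions, and nothing in the documents favours any of them.

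**The case against.** The strongest reply is that safeguards exist and the risk is small. Much of it stands.

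- **Symptomatic women are covered.** The listed symptoms trigger a calcium test whatever their cause.
- **There is a stop rule.** Section 3.0 names calcium and vitamin D as the tests and then stops treatment on any value pointing to toxicity. The natural reading includes calcium. What is missing is a number, and section 7.0 does not mention calcium.
- **Section 8.1 may list study tests only.** Section 3.0 says the study does not dictate the cancer treatment course, and 8.1 shows no blood counts or chemotherapy chemistry. Routine calcium may well be drawn. The documents neither show this nor require a result to be reviewed before dosing, so it reduces the practical gap without closing it.
- **The dose is called standard of care.** Whether the cited guideline expects calcium monitoring cannot be checked here, so no departure from it is claimed.

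Three stronger readings are tempting and are not supported:

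- **That the trial has no calcium safeguard at all.** The two section 3.0 provisions above contradict this.
- **That section 4.2.3 adds a separate hazard** by admitting "Patients taking vitamin D at the time of enrollment without a diagnosis of vitamin D deficiency". A woman who takes supplements is loaded only if her 25(OH)D is still below 20 ng/mL, and section 3.0 has medication reconciliation at every gynecologic oncology visit.
- **That calcium is also needed at the later 25(OH)D draws and in a new SAP table.** Those draws begin at completion of primary therapy and are not tied to loading. SAP section 8a already tabulates adverse events by preferred term and worst severity, so reported hypercalcemia would appear there.

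**Conclusion.** The point holds within limits. Before loading, the plan requires no calcium measurement, and it gives no numeric calcium value for stopping. Silent hypercalcemia, including undiagnosed primary hyperparathyroidism, therefore has no study-required check before 50,000 IU weekly begins.

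Severity is low. By the protocol's account toxicity from the dose is very unlikely, no rate of pre-existing hypercalcemia is given, and no number of affected women is claimed. A reader might infer that the trial's results are at risk. They are not: the comparison of repleted with unrepleted deficient women does not depend on calcium.

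The conclusion rests on the documents alone. If local practice already has calcium reviewed before the first dose, the change only writes that practice down.

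**What to change.** **1. Section 8.1.** Add albumin-corrected serum calcium at screening, run on the creatinine sample, at least for women with 25(OH)D below 20 ng/mL. Require review before the first vitamin D dose. A value above the laboratory's upper limit of normal defers vitamin D pending work-up and does not delay cancer treatment.

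**2. Sections 3.0 and 7.0.** State one calcium stop value beside the 25(OH)D limit. For example: vitamin D stops if albumin-corrected calcium is above the laboratory's upper limit of normal and this is confirmed on repeat testing. The repeat keeps a trivial single elevation from withdrawing treatment.

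**Cost.** One schedule row, one sentence in each of two sections, and the 25 to 100 calcium assays counted above, each with an albumin, on blood already drawn. No extra visit, procedure or staff is needed.

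**Downside.** A few incidental high values will need follow-up and may delay or stop vitamin D. In a group of about 25, each such woman matters to the amount of intervention delivered, which is a further reason to require confirmation before stopping.
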